Cover Page

Official Title:

Effectiveness of visual pedagogy-assisted tooth-brushing training among preschoolers with special needs for oral health promotion

Date: 2015.11.22

Background

Children with special needs are those who have physical, mental, sensory, behavioral, emotional, and chronic medical conditions that requires health care beyond that considered routine and which involves specialized knowledge, increased awareness, attention, and accommodation (Saravanakumar, et al.,2013).

Previous studies showed that people with special needs, such as intellectual disability, had poor oral health (Yuki Oda, et al., 2015), exhibiting a higher risk of developing caries than normal individuals. Although sealant, fluoride, and oral hygiene maintenance are effective ways to prevent dental caries, 30% of mental impaired patients have never received dental treatment (Oliveira et al., 2013). Individuals with disability have a significantly reduced ability to understand new or complex information (Ayub M, et al., 2015), and it is hard for them to cooperate with dental treatment (Maeda S, et al., 2005). Blomqvist et al. also demonstrated that children with learning problems had significantly more dental behavior management problems compared with a control group (Blomqvist M., et al., 2004), which would make routine dental care less achievable, resulting in poor oral health and the progression of existing oral diseases (Chang et al., 2014). Most of the dental diseases are originated by plaque, and increasing numbers of studies about oral health promotions are focused on plaque control, such as utilization of antibacterial agents, and special cleaning devices. Among them, the mechanical means for plaque control are much safer and more practical (Garbin C., et al. 2009). In addition, Liu Z et al. showed that toothbrushing more than twice a day is one of the caries-protective factors experience in disabled children (Liu Z., et al. 2014). Toothbrush is a universally accepted method for oral hygiene promotion among children with special needs. However, majority of children show noncompliance toward brushing and they try to hide themselves from daily brushing task, because they considered it as tedious procedure and dislike the brushing (Ganesh M., 2012). As for children with special needs, the situation is much worse.

Researchers have used visual pedagogy to show a structured method and technique of tooth brushing by series of pictures. The pictures were placed in the bathroom or wherever tooth brushing was performed, and the visual pedagogy was proved to be a useful tool in helping children with special needs to improve their oral hygiene (Pilebro c., et al. 2005). Goyal S. et al. even showed that for mentally challenged individuals, manual toothbrushes reinforced with audio-visual instructions for brushing might be comparable to the use of powered toothbrushes (Goyal, S. et al. 2011).

However, to date there has been limited researches focused on the effectiveness of toothbrushing assisted with visual pedagogy to promote oral health among special care communities. Community-based studies are necessary to provide reliable evidence to support or refute the interventions. In the proposed study, standard tooth-brushing training, along with a package of structured social stories illustrating the tooth-brushing procedure, healthy diets, and dental visit will be provided to preschool children with special needs. We hypothesized that oral-health related behaviours will be modified among children who receive visual-pedagogy (social story) -assisted tooth-brushing training, and thereby, their oral health status will be improved after intervention.

Method

Trial design

This study will be designed as a block-randomised controlled parallel blind clinical trial. Duration of the study will be 24 months.

Recruitment

Participants will be recruited from the Special Child Care Centers and Special Schools of The Spastics Association of Hong Kong (SAHK). Children aged from 2-6 years old with special care conditions such as Prader-Willi syndrome, intellectual disability (ID), autistic spectrum disorders (ASD), cerebral palsy (CP), Down's syndrome (DS), attention deficit hyperactivity disorder (ADHD), delayed development, or learning disorders will be invited to participant in this study. Consent form and information sheet will be delivered to children meet the above requirement. Only children with informed consent signed by parents will be recruited.

Exclusion criteria

Children manifested with at least one of the following conditions will be excluded from this clinical trial:

- Severe visually impaired
- Severe hearing impaired
- Severe physical disabled (cannot hold a toothbrush)
- Requiring emergent dental treatment
- Use of antibiotic within 3 months
- Dental prophylaxes in the last 6 months

Sample size calculation

The primary outcome is the development of new dental caries in the children over the 24-month study period. Based on the previous oral health promotion conducted among healthy preschool children in Hong Kong (Jiang M., 2013), the mean dmfs in control group and intervention groups are 0.3 (SD = 1.3), 0.2 (SD = 0.7), 0.4 (SD = 1.2). We assumed that the mean dmfs in control group and test group are 0.7 (SD = 1.0) and 0.3 (SD = 0.5). The program G* power 3.1.9.2 is used for sample size calculation: two-tail test, a =0.05, at a power of 95%. This give

a sample size target of 105 children per group. Considering 30% overestimation to allow for dropout in 2 years, totally 300 children will be invited, with 150 children per group.

Baseline information

Baseline information will consist of the following components:

- Clinical oral examination
- Tooth-brushing performance observation
- Questionnaire-based survey

Clinical oral examinations will be performed according to the following criteria: i) Caries status were assessed by the International Caries Detection and Assessment System(ICDAS); ii) Oral hygiene status by Simplified oral hygiene index of Greene and Vermilion (OHI-S); iii) gingival health status by Modified Gingival Index of Lobene (MGI). Dental examination will be performed at Special Child Care Centers by a pediatric dentist with a disposable mouth-mirror attached to an LED light. Tell- Show-Do (TSD) technique will be used to improve children's cooperation level. Tooth-brushing performance will be assessed by two observers. There will be 13 steps listed in the assessment form, steps which are performed by child or parent will be recorded respectively, as well as the total time for each tooth-brushing session. After dental examination and tooth-brushing assessment, a standard hands-on toothbrushing training will be provided immediately to each child and his/her parent. Oral health instruction will also be illustrated to the participants, reinforced by social stories or conventional leaflets. Questionnaires regarding children's oral health related behaviours, family demographic information and parents' oral health literacy assessment will be completed by parents, while questionnaires assessing children's developmental profile will be filled by staff in Special Child Care Centers.

Allocation

3

Concealed block randomization at school levels will be used to allocate subjects into 2 group. The randomised sequence will be generated by an investigator who do not participate in the outreach service. The allocation sequence will be sealed in an envelope, and opened at the Special Child Care Centres by an assistant, who will also be responsible for delivering the materials to children and their parents. Hence, children (participant) and investigators (outcome assessor) will not know the randomised sequence. After a standard tooth-brushing training and oral health instruction, Group 1 will be set up as a positive control, receiving standard oral-health education leaflets issued by the local government, while Group 2 will act as test group, receiving social stories developed and validated by the investigators.

Follow-up appointments

Commercially available toothbrushes and fluoridated toothpaste will be delivered to each child and renewed at every three months. Meanwhile, the old toothbrush and remaining toothpaste will be returned, and toothpaste usage and toothbrush wear will be monitored. Follow-up assessments will be performed at 6-month, 12-month, 24-month. Education materials about "healthy diets" will be emphasized at 6-month follow-up, and dental-visit related education materials will be emphasized at 12-month follow-up. Tooth-brushing training was reinforced at each follow-up appointment. Education material about tooth brushing, healthy diets and dental visit will be illustrated to children and their parents, and parents will be encouraged to read those materials to their children in their daily lives. Oral examination and tooth-brushing assessment in follow-up appointment will be performed using the same methods and criteria as baseline; all parents or primary caregivers will complete a set of questionnaires on their attitudes towards the interventions and their children's oral-health related behaviours.

Significance

The present study will provide scientific evidence of effective oral health care for children with special needs. Meanwhile, the interventions adopted in the control group and test group have potential benefits to encourage the children with special needs to take care of themselves by learning tooth brushing independently at an early age status, supporting their relatively independent life in the future.

References

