Statistical Analysis Plan

Official Title:

Effectiveness of visual pedagogy-assisted tooth-brushing training among preschoolers with special needs for oral health promotion

Date: 2015.11.22

All the data will be analysed using IBM SPSS. Variables from the questionnaires will be analysed by t test for independent samples or its non-parametric equivalent for continuous data and Chi-square tests for categorical data. Descriptive statistics of cooperation with tooth brushing in each group will be determined and variations in cooperation with tooth-brushing and developmental level of special needs will be determined by Chi-square statistics. McNemar's test will be used to analyse whether children's oral-health related behaviours will be changed before and after intervention. Then regression analyses will be conducted to determine developmental factors associated with children's oral health status or cooperation in conducting tooth brushing, accounting for child's age and gender in the model. Variations in simplified oral hygiene index, modified gingival index, caries incidence, number of completed tooth brushing tasks and time taken to complete the overall task will be determined using repeated measures ANOVA (or Friedmann ANOVA for nonparametric data). Inter-group comparisons of the above outcome variables with respect to baseline will be determined using paired t-test (or Wilcoxon signed rank for nonparametric data). Intra-group comparisons of at baseline, 6-month, 12-month, and 24-month will be conducted using student's t-test (or Mann Whitney U test for nonparametric data). Magnitude of change will be derived through effect size calculation (mean change/ SD of baseline values) to provide an indication of clinical significance of the results. The significance levels will be set to be $P < 0.05$.

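### The protocol does not say whether schools or children are randomised, and neither the sample size nor any between-group test accounts for school

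*Protocol*

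**What the plan says.** The protocol's Allocation section states: "Concealed block randomization at school levels will be used to allocate subjects into 2 group". It adds: "The allocation sequence will be sealed in an envelope, and opened at the Special Child Care Centres by an assistant". It does not say whether an assignment is drawn for each child or for each centre. The Trial design section calls the study a "block-randomised controlled parallel blind clinical trial" and mentions no clusters.

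The Sample size calculation section assumes mean dmfs of 0.7 (SD 1.0) in the control group and 0.3 (SD 0.5) in the test group, with "two-tail test, a =0.05, at a power of 95" per cent. It arrives at "a sample size target of 105 children per group" and inflates this to 150 for 30% dropout. It gives no number of centres, ICC or design effect.

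The SAP analyses questionnaire variables by "t test for independent samples or its non-parametric equivalent for continuous data and Chi-square tests for categorical data". For the clinical outcomes it says that "caries incidence, number of completed tooth brushing tasks and time taken to complete the overall task will be determined using repeated measures ANOVA", or Friedman's test as the non-parametric alternative. It also lists Student's t or Mann-Whitney tests at each visit, and regressions adjusted for age and gender. School appears in none of these.

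**The concern.** The Allocation sentence names the school as the level of randomisation and the child as the thing allocated. Each reading calls for a different analysis, and the SAP provides neither.

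If whole schools are allocated, children in one school share an arm and also a setting: they are recruited, examined and given their materials through the centre. Any positive correlation of outcomes within a centre then makes child-level standard errors too small. The between-group test on new caries, the primary outcome, would reject a true null more than 5% of the time, and 105 children per group would carry less information than the power calculation supposes. A false finding that social stories prevent caries becomes more likely.

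If children are blocked within school, both arms are present in each school and the school effect largely cancels from the comparison. Leaving school out then makes the tests slightly conservative.

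The point concerns between-group comparisons only. McNemar's test and the paired t and Wilcoxon signed-rank tests compare a child with itself and are not part of it.

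**Working it through.** **1. The plan's own figure.** Inputs from the Sample size calculation section: means 0.7 and 0.3, SDs 1.0 and 0.5, two-sided 5%, 95% power.

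- Pooled SD = √((1.0² + 0.5²)/2) = 0.791, so d = 0.4/0.791 = 0.506.
- The noncentral t gives 103 per group (power 95.1%). At 105 per group, power is 95.4%. With d rounded to 0.5, the answer is exactly 105.
- 105/0.7 = 150 invited per group.

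The stated figures reproduce with independent children, that is, with a design effect of 1. Dropout is the only inflation.

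**2. If whole schools are allocated.** The documents give neither the number of centres K nor the ICC, so these are assumptions: K = 12 or 20 equal centres, ICC 0.02 or 0.05, 210 analysed children (2 × 105), hence m = 210/K = 17.5 or 10.5 children per centre.

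- Design effect: DE = 1 + (m − 1) × ICC.
- True error of the naive 5% test: 2 × (1 − Φ(1.96/√DE)).
- Power of a valid test: the t-test calculation in step 1 with 105/DE per group, then again with K − 2 degrees of freedom.
- Children needed per group for 95% power: 103 × DE. Invited: that number divided by 0.7.

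| K | ICC | DE | Naive error | Power | Power, K − 2 df | Needed per group | Invited per group |
|---|---|---|---|---|---|---|---|
| 20 | 0.02 | 1.19 | 7.2% | 91.7% | 88.8% | 123 | 176 |
| 20 | 0.05 | 1.475 | 10.7% | 85.0% | 81.4% | 152 | 218 |
| 12 | 0.02 | 1.33 | 8.9% | 88.5% | 81.7% | 137 | 196 |
| 12 | 0.05 | 1.825 | 14.7% | 76.8% | 68.7% | 188 | 269 |

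The last two columns hold centre size fixed and leave out the further penalty for few centres, so they are on the low side. A simulation (20,000 runs, normal outcome, equal centres) agreed. Naive error ran from 7.3% to 15.1%. A t test on centre means had error of 4.9% to 5.2% and power of 88.8% down to 69.4%.

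**3. A wider range.** With 5 to 30 children per school and ICC 0.01 to 0.05, DE runs from 1.04 to 2.45. By the normal approximation, naive error runs from 5.5% to 21.1%, and power at 105 per group from 94.9% down to 64.9%. The direction is the same for every positive ICC; the size depends on two quantities that the plan omits.

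**4. If children are blocked within school.** The true standard error is √(1 − ICC) times the naive one, so the naive error is 1/√(1 − ICC) = 1.010 to 1.026 times too wide for ICC 0.02 to 0.05. The test's error is 2 × (1 − Φ(1.96/√(1 − ICC))) = 4.8% to 4.4% and power is about 96%. Simulation gave 4.6% to 5.0% error and 95.5% to 95.6% power.

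**The case against.** The best reply is that the documents lean towards the child as the unit. Subjects are the object of the allocation sentence, clusters are never mentioned, and 150 per group comes readily from blocking children but not from allocating schools of unequal size. On that reading nothing is invalid, by the figures above. This is a reasonable inference, but the protocol does not state it, and a reader can equally take the sentence to mean that schools are allocated. The SAP omits school on either reading.

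The size of the effect rests on assumed inputs, and low values give mild results: 20 centres at ICC 0.01 gives 6.1% error and about 94% power. Individual training, home reading and examinations by a paediatric dentist may all keep the ICC low. That stands, and the figures are illustrations, not estimates.

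The error and power columns also describe different tests. The naive test would still reject about 94% to 90% of the time under the planned effect in these scenarios, but only by having an inflated error rate. The calculations further assume normal outcomes, while the planned means and SDs suggest skewed counts.

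Finally, the SAP attaches its paired tests to inter-group comparisons and its two-sample tests to intra-group ones, and names no group factor in the ANOVA. I have classed the tests by what they compute. The labels look reversed, which is a separate matter.

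**Conclusion.** The concern holds, in conditional form. It is certain that the unit of randomisation is unstated, that 105 per group assumes independent children, and that no between-group analysis includes school. It is not certain that error and power are affected: that needs whole-school allocation and a positive ICC.

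If both apply, with 12 to 20 equal centres and ICC 0.02 to 0.05, the 5% test is really a 7% to 15% test. The 95% power becomes 92% to 77%, or 89% to 69% on centre-level degrees of freedom. Keeping 95% would take about 123 to 188 analysed children per group, against 105. If children are blocked within school, the cost is a small loss of precision.

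This must be fixed because the validity of the primary comparison turns on a fact the protocol omits, and too few centres or children cannot be made good at the analysis stage.

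**What to change.** 1. In Allocation, state whether the school or the child is the unit of randomisation. This is one sentence.
2. In the SAP, name school as an analysis variable and include it in every between-group analysis. If schools are allocated, use a mixed model with a random school effect, or GEE clustered on school, with a small-sample correction. If children are blocked within school, use school as a stratum.
3. Leave the within-child tests as they are.
4. If schools are allocated, also give the number of centres and restate power with a design effect over a stated ICC range. The sponsor then either accepts the lower figure or plans for more children or centres.

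The cost is a sentence, some SAP wording and one model term. Children are recruited through identified centres, so recording school should be simple. With within-school blocking the price is a few degrees of freedom. With whole-school allocation it is a less favourable power figure or a larger trial.

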Statistical Analysis Plan

Official Title:

Effectiveness of visual pedagogy-assisted tooth-brushing training among preschoolers with special needs for oral health promotion

Date: 2015.11.22

All the data will be analysed using IBM SPSS. Variables from the questionnaires will be analysed by t test for independent samples or its non-parametric equivalent for continuous data and Chi-square tests for categorical data. Descriptive statistics of cooperation with tooth brushing in each group will be determined and variations in cooperation with tooth-brushing and developmental level of special needs will be determined by Chi-square statistics. McNemar's test will be used to analyse whether children's oral-health related behaviours will be changed before and after intervention. Then regression analyses will be conducted to determine developmental factors associated with children's oral health status or cooperation in conducting tooth brushing, accounting for child's age and gender in the model. Variations in simplified oral hygiene index, modified gingival index, caries incidence, number of completed tooth brushing tasks and time taken to complete the overall task will be determined using repeated measures ANOVA (or Friedmann ANOVA for nonparametric data). Inter-group comparisons of the above outcome variables with respect to baseline will be determined using paired t-test (or Wilcoxon signed rank for nonparametric data). Intra-group comparisons of at baseline, 6-month, 12-month, and 24-month will be conducted using student's t-test (or Mann Whitney U test for nonparametric data). Magnitude of change will be derived through effect size calculation (mean change/ SD of baseline values) to provide an indication of clinical significance of the results. The significance levels will be set to be $P < 0.05$.

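### The developmental regression has no centre term although centre staff rate the developmental profile, so its coefficients can mix centre differences with developmental associations

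*SAP*

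**What the plan says.** - **Sites** (protocol, Recruitment): "Participants will be recruited from the Special Child Care Centers and Special Schools" of one organisation. The number and size of the sites are not given.
- **Who rates development** (protocol, Baseline information): "questionnaires assessing children's developmental profile will be filled by staff in Special Child Care Centers". No common rater and no calibration across centres is described. In the same section, the dental examination is assigned to a paediatric dentist and the brushing assessment to two observers.
- **Regression** (SAP): "regression analyses will be conducted to determine developmental factors associated with" oral health or cooperation with brushing, "accounting for child's age and gender in the model".
- **Chi-square** (SAP): variation in cooperation and "developmental level of special needs will be determined by Chi-square statistics". No stratification is mentioned.
- **Allocation** (protocol, Allocation): "Concealed block randomization at school levels will be used to allocate subjects into 2 group".

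Neither document names a centre or rater term, a random effect, a stratified test or a clustered standard error for any analysis.

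**The concern.** The predictor here is observed, not randomised, so nothing in the design balances developmental level across centres. The natural reading, though not stated outright, is that staff rate the children of their own centre. The score then carries a centre component from two sources: centres differ in the children they take, and staff differ in how strictly they rate. Recruitment spans child care centres and special schools, with conditions from learning disorders to cerebral palsy, so different case mix is plausible even if every rater used the form identically.

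If the outcome also differs by centre, two things go wrong in a model without centre. First, children in a centre are not independent, so the standard error of the developmental coefficient can be too small. Second, the coefficient combines the association among children within a centre with differences between centres. The second problem is confounding, and a corrected standard error would not remove it. At stake is the SAP's statement of which developmental factors go with oral health or cooperation.

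**Working it through.** **The plan's own figure.** The documents give no figure for the developmental analyses. The sample size serves only to set the range of N, and it reproduces. With SD = √((1.0² + 0.5²)/2) = 0.791, d = 0.4/0.791 = 0.506. At two-sided 0.05 and 95% power, n per group is 102 (normal), 103 (t) or 108 (Wilcoxon), against the stated 105. Then 105/(1 − 0.30) = 150 per group. So N lies between 210 evaluable and 300 invited.

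**Assumptions, not in the documents.** These are the number of centres, the children per centre (m), ICC_x (share of variance in the rating that lies between centres) and ICC_y (the same share for the outcome).

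**Formula.** With no true association and independent centre effects in rating and outcome, the variance of the slope is inflated by about V = 1 + (m − 1) × ICC_x × ICC_y. The nominal 5% test then rejects with probability of about 2 × [1 − Φ(1.96/√V)].

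Example with 10 centres of 30, ICC_x = 0.2, ICC_y = 0.1: V = 1 + 29 × 0.02 = 1.58, √V = 1.257, 1.96/1.257 = 1.559, rejection about 11.9%. The reported standard error is 1/1.257 = 0.80 of what it should be.

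**Simulation of the linear regression** (20,000 runs per setting, no true association; age and gender left out because they carry no centre information in this setup):

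| Centres × children | ICC_x / ICC_y | V | Rejects, no centre | Rejects, centre as fixed effect |
|---|---|---|---|---|
| 15 × 20 | 0.1 / 0.1 | 1.19 | 6.9% | 5.1% |
| 10 × 30 | 0.1 / 0.1 | 1.29 | 8.2% | 5.1% |
| 10 × 21 | 0.2 / 0.1 | 1.40 | 9.3% | 4.9% |
| 10 × 30 | 0.2 / 0.1 | 1.58 | 11.0% | 5.1% |
| 6 × 35 | 0.2 / 0.1 | 1.68 | 11.8% | 5.0% |
| 10 × 30 | 0.3 / 0.1 | 1.87 | 14.1% | 5.0% |
| 10 × 30 | 0.05 / 0.05 | 1.07 | 5.5% | 4.8% |

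Smaller sets of 2,000 to 3,000 runs agree within simulation error (9.8% and 12.2% for 10 × 30 at 0.2/0.1; 6.4% for 15 × 20 at 0.1/0.1; 14.9% for 10 × 30 at 0.3/0.1).

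**Outside that range** (3,000 runs, N = 300). With ICC_x = 0 and ICC_y = 0.05 in 10 centres the rate is 5.3%, so both variables must be clustered. Twenty centres at 0.2/0.1 give 7.4%. Six centres of 50 give 15.8% at 0.2/0.1 and 18.0% at 0.3/0.1.

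**Chi-square.** For a 3 × 2 table with 10 centres at 0.2/0.1, the rate is 6.9% at N = 300 and 5.2% at N = 210. A binary outcome with 6 to 15 centres, ICC_x 0.1 to 0.2 and ICC_y 0.1 on the latent scale gives 5.4 to 7.9%. It reaches about 10% only in harsher settings (6 × 50 at 0.2/0.1: 10.3%; 10 × 30 at 0.3/0.1: 10.0%).

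**Logistic regression without centre**, under the same binary-outcome assumptions: 6.0 to 9.9%.

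These simulations measure error rates only. If one cause, such as case mix, moves ratings and outcomes together across centres, the coefficient is also biased. The documents give no basis for sizing that.

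**The case against.** - **The size is assumed throughout.** This stands. The documents give neither the number of centres nor the ICCs, and at 0.05/0.05 there is almost nothing to correct.
- **The plan limits outcome differences between centres.** A dentist examines to named indices, two observers score brushing on a 13-step form, and all children get standard training and supplied toothbrushes and toothpaste. This reduces measurement differences in the outcome. It does not remove differences in case mix or in centre routine, and it does nothing for the staff-rated predictor.
- **The 6 to 15% range belongs to a continuous outcome.** This stands. The SAP tests cooperation by Chi-square, which suggests a categorical variable, and the Chi-square and logistic figures are lower. A reader might infer that both planned analyses are equally prone to false positives; the calculations do not support that.
- **Fixed effects have a price.** This stands. Real developmental differences between centres and schools are discarded along with rater differences. With a binary outcome at an assumed 20% prevalence, at least one centre had no outcome variation in 18 to 36% of simulated datasets with 10 centres and 54 to 78% with 15. Such centres drop out of a fixed-effect logistic model or a stratified test. Cluster-robust standard errors avoid this, but they repair only the standard error and leave the confounding.
- **The analysis is secondary.** This stands. The primary outcome is new caries and the hypothesis concerns the intervention.

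A reader might also infer that leaving school out of the treatment comparison is harmless because arms are balanced within each school. The Allocation section does not support this: its wording does not settle whether children within schools or whole schools are allocated. This point takes no position on the treatment comparison.

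**Conclusion.** The concern holds for the developmental regression, in conditional form. As specified, the model cannot separate a developmental association from differences in case mix or rater strictness between centres, and its p-values can be too small. For a linear regression with 6 to 15 centres of 20 to 35 children, rating ICC 0.1 to 0.3 and outcome ICC 0.1 (all assumed), the false positive rate is about 6 to 15%, against about 5% with centre included. The Chi-square is the weaker half, at about 5 to 8% over most of that range. The documents do not show that inflation will occur, only that the plan has no protection against it. The sample size is unaffected. The change is worth making because it is cheap and because choosing the adjustment after seeing the data would weaken the result.

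**What to change.** State in the SAP that the developmental regression includes centre (school) as well as age and gender. Use a fixed effect for continuous outcomes. Where a categorical outcome leaves centres sparse, use a random effect or a conditional model, and name the choice in advance. A random effect keeps all centres but lets some between-centre information back into the coefficient; a conditional model drops centres without outcome variation.

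Base conclusions about developmental level and cooperation on that centre-adjusted model, or on a centre-stratified test (Cochran-Mantel-Haenszel) if strata are large enough. Keep the pooled Chi-square as descriptive.

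The cost is a sentence or two of SAP text and no new data, since each child's centre is known and SPSS fits these models. With 6 to 15 centres, fixed effects use 5 to 14 degrees of freedom out of 210 to 300 children and give up the between-centre information.

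### With 30% dropout allowed for, repeated measures ANOVA/Friedman keeps only children seen at every visit, and nothing carries leavers' earlier results into the 24-month comparison

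*SAP*

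**What the plan says.** The protocol's sample size section makes new caries over 24 months the primary outcome. It sets "a sample size target of 105 children per group" and then inflates: "Considering 30% overestimation to allow for dropout in 2 years, totally 300 children will be invited, with 150 children per group". Follow-up assessments are at 6, 12 and 24 months (protocol, Follow-up appointments).

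The SAP is a single paragraph. For OHI-S, MGI, caries incidence, brushing steps completed and brushing time, it says that variation "will be determined using repeated measures ANOVA (or Friedmann ANOVA for nonparametric data". It adds paired t-tests (or Wilcoxon signed rank) against baseline, and two-sample t-tests (or Mann-Whitney) at baseline, 6, 12 and 24 months. The labels inter-group and intra-group appear to be swapped between those two sentences. I read the two-sample tests as the comparison between arms at each visit.

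Neither document names an analysis set, a missing-data method, imputation, a mixed model or a sensitivity analysis. Neither restricts the analysis to children who complied.

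**The concern.** Classical repeated measures ANOVA and the Friedman test work on complete rows. A child examined at baseline, 6 and 12 months who then leaves is removed from the longitudinal analysis, and so is a child who misses or refuses one examination. The two-sample test at 24 months uses only children present at 24 months, and takes nothing from what was seen earlier in those who left.

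Inflating the sample replaces the lost numbers, but it does not make those who remain representative of those randomised. In preschoolers with special needs, poor cooperation or existing dental disease could plausibly make a child likelier to leave or refuse examination. If so, the completers' difference need not equal the difference between the arms as randomised. The 6- and 12-month results that could correct for this are collected, but they do not enter the 24-month comparison. The separate tests also run on different subsets, so a pattern across visits mixes true change with change in who is present.

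**Working it through.** **1. The plan's own figures.** Inputs (protocol, Sample size calculation): "We assumed that the mean dmfs in control group and test group are 0.7 (SD = 1.0) and 0.3 (SD = 0.5"), and "two-tail test, a =0.05, at a power of 95"%.

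- Pooled SD = √((1.0² + 0.5²)/2) = 0.791; d = 0.4/0.791 = 0.506.
- Normal approximation: n = 2 × (1.960 + 1.645)² × 0.625/0.4² = 101.5, so 102 per arm. The noncentral t gives 103, or 105 with d rounded to 0.5. The stated 105 reproduces.
- Inflation: 105/(1 − 0.30) = 150 per arm, as stated. The allowance is 150 × 0.30 = 45 leavers per arm.
- Power with 105 completers per arm is 95.4% (t-test), so power is not the issue.

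**2. Observed results unused in the longitudinal analysis.** Assume that 150 per arm are randomised, 45 leave by month 24, and stayers miss no visit. With n6 and n12 children seen at 6 and 12 months, the unused results per arm are (n6 − 105) + (n12 − 105), out of n6 + n12. The documents do not give the timing of dropout, so I show a range:

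| Timing of dropout | n6 | n12 | Unused | Share |
|---|---|---|---|---|
| All before month 6 | 105 | 105 | 0 of 210 | 0% |
| Equal thirds per interval | 135 | 120 | 45 of 255 | 18% |
| Constant over time | 138.75 | 127.5 | 56.25 of 266.25 | 21% |
| All after month 12 | 150 | 150 | 90 of 300 | 30% |

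**3. Possible bias in the completers' 24-month difference.** Assumptions: the plan's means; half of new caries present by month 12; dropout of 50% if there is any new caries by month 12 and 25% otherwise. The chance of staying is then 0.50, plus a further 0.25 if there is none by month 12.

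*Control: gamma-Poisson, mean 0.70, variance 1.00.*
- Shape k = 0.7²/(1.00 − 0.70) = 1.633.
- P(none by month 12) = (1 + 0.35/1.633)^−1.633 = 0.728.
- Mean later count given none = 0.35/1.214 = 0.288.
- Staying = 0.5 + 0.25 × 0.728 = 0.682, so dropout is 32%.
- Completers' mean = (0.5 × 0.70 + 0.25 × 0.728 × 0.288)/0.682 = 0.590.

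*Test: binomial, n = 2, p = 0.15 (mean 0.30, SD 0.505, close to the plan's 0.5).*
- P(none by month 12) = 0.925² = 0.856.
- Mean later count given none = 2 × 0.075/0.925 = 0.162.
- Staying = 0.5 + 0.25 × 0.856 = 0.714, so dropout is 29%.
- Completers' mean = (0.5 × 0.30 + 0.25 × 0.856 × 0.162)/0.714 = 0.259.

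*Results.*
- Same mechanism in both arms: difference 0.590 − 0.259 = 0.33, against a true 0.40. Ratio 0.259/0.590 = 0.44, against 0.3/0.7 = 0.43.
- Selective dropout in the control arm only: difference 0.590 − 0.30 = 0.29. Ratio 0.30/0.590 = 0.51.

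**4. Whether the earlier visits would help.** A separate simulation used a continuous outcome with unit SD, correlation 0.5 between visits, a true 24-month difference of −0.50, about 30–40% dropout, and dropout driven by the last observed result. The completers' difference was −0.50 with random dropout, −0.48 with the same mechanism in both arms, −0.37 with selection in one arm and −0.21 with opposite mechanisms. A likelihood estimate using the 6- and 12-month results stayed at about −0.50 throughout. That last result is expected, because dropout here depends only on observed data.

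**The case against.** Three stronger readings are tempting, and the documents support none of them.

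- *That every 6- and 12-month result from leavers is thrown away.* A reader might infer this from the ANOVA sentence alone. The SAP also plans tests at 6 and 12 months and paired tests against baseline, and these can use children who leave later.
- *That the trial's answer describes only fully attending, fully treated children, in effect a per-protocol result.* Complete attendance is required only by ANOVA/Friedman, which the SAP does not name as the primary analysis. The 24-month test needs only month 24, plus baseline for change. A child who leaves after month 12 was offered both the diet and the dental-visit material, yet is excluded from the ANOVA. Attending a visit does not show that the material was used at home.
- *That 45 children per arm lose all their follow-up data.* A child who leaves before month 6 has none to lose, and 30% is an allowance rather than an observed rate.

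It is also fair to say that the dropout rates of 50% and 25% are invented, and that with the same mechanism in both arms the ratio barely moves and the difference shrinks towards zero. One could add that stating an analysis set and a missing-data rule might be enough.

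These objections limit the point without removing it. The longitudinal method still needs complete rows, and no planned analysis brings leavers' earlier results into the 24-month comparison between arms. A stated analysis set would not change what ANOVA and Friedman do with incomplete rows.

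**Conclusion.** The concern holds in this limited form and should be acted on. By the plan's own allowance, 105 of 150 children per arm would remain for a longitudinal analysis that requires every visit, and fewer if any of them miss an intermediate examination. Between 0 and 30% of observed 6- and 12-month results would go unused there, about 18–21% if dropout is spread evenly.

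The complete-row requirement, the 30% allowance and the absence of any missing-data method can be read directly from the documents and the named methods. Bias is a risk of unknown size. It is nil if dropout is unrelated to outcome, modest on the difference scale (0.33 against 0.40) under the assumed common mechanism, and larger (0.29) if selection acts in the control arm only. The documents do not say which applies.

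**What to change.** Replace repeated measures ANOVA/Friedman with a mixed-effects model that uses every available visit of every randomised child, analysed as allocated, with arm, visit, arm-by-visit and age.

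- Continuous outcomes: SPSS MIXED.
- New-caries counts: a log-link count model with robust standard errors (GENLINMIXED or GEE) that does not force overdispersion. The plan's test-arm variance (0.5² = 0.25) is below its mean (0.30), which a negative binomial cannot represent. If GEE is used, combine it with multiple imputation.
- Read the arm difference at month 24 from this model.
- State the analysis set, and report the completer analysis as a sensitivity analysis.

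The cost is SAP wording and a different procedure in the software already named, with no new children, visits or data. The small downside is reliance on a missing-at-random assumption, which is weaker than the assumption that complete-case analysis needs.
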